3.2 Secondary Objectives

- To compare the quality of life (QOL) in patients who received nintedanib versus placebo during active treatment until 6 months after completion of treatment.
- To compare the progression-free survival, overall survival and 1-year progression-free survival rate in patients who received nintedanib versus placebo.
- To compare pulmonary function test (PFT) results and RP score in patients who received nintedanib versus placebo.
- To compare the composite index (based on PFT, RP score and QOL) at the end of active treatment and 6 months after completion of treatment between patients who received nintedanib versus placebo.

3.3 Exploratory Objective:

- To investigate blood-based biomarkers in evaluating risk of developing radiation pneumonitis as well as the efficacy of nintedanib.

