13.7 Secondary Analyses

The OS and PFS will be reported by study arm using standard Kaplan-Meier methods. Comparisons of OS and PFS between study arms may utilize the two-sided stratified log-rank test. With a sample size of $n = 33$ in the control and $n = 66$ in the treatment group, there is an 80% chance of detecting a hazard ratio of 0.53 or smaller (with two-sided alpha of 0.05). If the

median PFS in the placebo arm is approximately 2 months, then this would be equivalent to detecting an increase in PFS of at least 1.75 months.

The overall and sub-category QOL and symptom scores (ranging from 0 to 68) will be reported by study arm and time using the appropriate descriptive statistics. Changes in the QOL and symptom scores may be compared between study arms using the Wilcoxon rank sum or independent sample t-tests, as appropriate. No adjustments for multiple testing will be made as this is a secondary analysis. With this sample size, there will be an 80% chance of detecting a change of at least 0.5 standard deviations. A 0.5 standard deviations is equivalent to approximately 9.1 points for the overall QOL and symptoms score; therefore, this study should be able to identify clinically relevant changes in QOL (59).

The PFTs will be reported by study arm and time using the appropriate descriptive statistics. Changes in PFTs, relative to baseline, will be evaluated within each study arm using the Wilcoxon signed rank or paired t-tests, as appropriate. Changes in PFTs may be compared between study arms using the Wilcoxon rank sum or independent sample t-tests, as appropriate. No adjustments for multiple testing will be made as this is a secondary analysis. With this sample sizes, we will have an 80% chance of detecting a change of at least 0.5 standard deviations.

The RP scores will be reported by study arm and time using the appropriate descriptive statistics. Changes in RP scores, relative to baseline, will be evaluated within each study arm using the Wilcoxon signed rank or paired t-tests, as appropriate. Changes in RP scores may be compared between study arms using the Wilcoxon rank sum or independent sample t-tests, as appropriate. No adjustments for multiple testing will be made as this is a secondary analysis. With our sample sizes, we will have an 80% chance of detecting a change of at least 0.5 standard deviations.

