fashion using multivariate logistic regression, such that the resulting model predicts the probability of radiation pneumonitis. A set of candidate variables will be obtained from miR expressions and relevant patient characteristics (demographic and clinical). Standard variable reduction techniques will be applied if the number of candidate variables grows large. The variables in the final model will be selected from the set of candidate variables, including possible two-way interaction terms, using forward selection (alpha entry = 0.05) followed by backward elimination (alpha exit = 0.05). Models are fit using Firth's penalized function and model assumptions are verified graphically. Standard bootstrap and cross-validation techniques will be used to calibrate model coefficients. Model performance will be evaluated using calibration plots, receiver operating characteristic (ROC) curves, area under the ROC curve (AUC) and a decision curve. In both models the Youden's index method can also be used to determine the optimal threshold probability for classifying patients, from which standard classification measures can be obtained (sensitivity, specificity, positive predictive value and negative predictive values). As an alternative modeling strategy, classification and regression tree (CART) analysis may also be considered to develop a model using only the miR expressions. These analyses will be repeated using vitamin D, cytokine and mitochondrial DNA levels, alone and in combination with miR expression, to develop classification models.

All secondary analyses will be conducted in SAS v9.4 (Cary, NC), except for CART analysis conducted in R v2.12, at a significance level of 0.05.

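### The 80% power stated for a 0.5 SD change in QOL is about 64% (two-sided) on the only QOL test planned, and the PFT and RP score figures fit only a within-arm test

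*Combined protocol and SAP*

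**What the plan says.** Section 3.2 frames all three endpoints as comparisons between the randomised arms: "To compare the quality of life (QOL) in patients who received nintedanib versus placebo" and "To compare pulmonary function test (PFT) results and RP score in patients who received nintedanib versus placebo".

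Section 13.7 gives arm sizes of 33 (control) and 66 (treatment) and then treats each endpoint in turn.

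- **QOL.** Apart from descriptive statistics, one kind of test is listed: "Changes in the QOL and symptom scores may be compared between study arms using the Wilcoxon rank sum or independent sample t-tests, as appropriate". The power sentence follows: "With this sample size, there will be an 80% chance of detecting a change of at least 0.5 standard deviations". The section equates 0.5 SD with about 9.1 points on the overall score and concludes: "therefore, this study should be able to identify clinically relevant changes in QOL (59").
- **PFT.** A within-arm test comes first: "Changes in PFTs, relative to baseline, will be evaluated within each study arm using the Wilcoxon signed rank or paired t-tests, as appropriate". A between-arm rank sum or t-test is listed as something that may be done. The same 80% at 0.5 SD is stated.
- **RP score.** The same pair of tests, then: "With our sample sizes, we will have an 80% chance of detecting a change of at least 0.5 standard deviations".

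The level for all secondary analyses is given once, at the end of the section: "except for CART analysis conducted in R v2.12, at a significance level of 0.05". None of the three power sentences says which test is meant, whether it is one- or two-sided, or whether the SD is that of the raw score or of its change. The PFS and OS power statement in the same section does give a two-sided alpha.

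**The concern.** A 1:2 split of 99 patients has the precision of a balanced trial of 44 per arm (33 × 66 / 99 = 22 = 44/2), and 44 per arm is too few for 80% power at half a standard deviation in a two-sample comparison. For QOL no other kind of comparison is planned, so the 80% has no listed test to rest on.

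The sentence carries weight because an explicit claim about clinical relevance is drawn from it. A reader would take it that an effect of 0.5 SD has a 20% chance of being missed. If the chance is nearer 36%, a null QOL result could be over-read as evidence that there is no relevant effect. For PFT and RP score, the plan gives no power for the comparison named in the objective.

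**Working it through.** **Inputs**
- Arm sizes 33 and 66 (Section 13.7; the 1:2 ratio and the total of 99 are in Section 13.1).
- Effect 0.5 SD, stated power 80%, level 0.05 (Section 13.7).
- Sidedness is not stated for these endpoints, so both are computed.
- Implied QOL SD: 9.1 / 0.5 = 18.2 points.
- Section 13.7 makes no allowance for missing data, so the full 33 and 66 are used except where noted.

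**1. Looking for the plan's 80%**

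A paired t-test with n = 33 has noncentrality 0.5 × √33 = 2.872 on 32 df, with two-sided critical value 2.037. Power is 79.5%, which fits the stated figure. It is a within-arm test in the placebo arm alone. The same test with n = 66 (noncentrality 4.062) has 97.9%. It is planned for PFT and RP score but not for QOL.

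A second match is a 1:1 split of the 99 patients tested one-sided: 79.5% by t-test, 80.0% by normal approximation. That contradicts the 1:2 allocation, and two-sided it gives only 69.2%.

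**2. The between-arm test at 33 versus 66**

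Noncentrality = 0.5 × √(33 × 66 / 99) = 0.5 × √22 = 2.345 on 97 df.

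| Test, 0.5 SD of change | Two-sided | One-sided |
|---|---|---|
| t critical value | 1.985 | 1.661 |
| t-test power | 64.1% | 75.3% |
| Rank sum power, normal data | about 62% | about 73% |

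The chance of missing the effect with the t-test is 100 − 64.1 = 35.9% two-sided, or 100 − 75.3 = 24.7% one-sided.

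**3. What 80% power would need**

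| Quantity | Two-sided | One-sided |
|---|---|---|
| Detectable difference at 33/66, in SDs of change | 0.603 | 0.534 |
| In QOL points, if 18.2 is the SD of change | 0.603 × 18.2 = 11.0 | 0.534 × 18.2 = 9.7 |
| Patients at 1:2 to keep 0.5 SD | 48 + 96 = 144 (80.2%) | 38 + 76 = 114 (80.4%) |

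The patient numbers show the size of the gap; they are not a proposal to enlarge the trial.

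**4. If 18.2 is instead the raw-score SD**

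With correlation r between baseline and follow-up, the SD of change is 18.2 × √(2(1 − r)), so the standardised effect is 0.5 / √(2(1 − r)). The documents give no r; the values below are assumptions.

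| r (assumed) | Effect in SDs of change | Two-sided power | One-sided power |
|---|---|---|---|
| 0.3 | 0.423 | 50.1% | 62.7% |
| 0.5 | 0.500 | 64.1% | 75.3% |
| 0.7 | 0.645 | 85.0% | 91.3% |

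Power reaches 80% at r of about 0.66 two-sided or 0.56 one-sided.

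**5. Missing data**

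With 10% or 20% of patients missing in each arm (assumed), two-sided t-test power at 0.5 SD of change falls to 59.5% or 54.4%.

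**The case against.** The strongest objection is that the 64% depends on which SD is meant, and the plan does not say. The 9.1 points come by way of a cited source that is not part of the documents. If they are half a raw-score SD, a strong enough correlation between baseline and follow-up brings the planned test to 80% or more. This stands as a condition on the figures: 64% and 75% apply to 0.5 SD of change. It does not rescue the sentence, because the plan states neither the SD nor a correlation, and a lower correlation would put power well below 64%.

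A second objection is that the origin of the 80% for PFT and RP score is unknown. It might come from the paired test, or from a balanced, one-sided calculation that does not match the design. That is fair, and the statistician should confirm the source. Whatever it was, 79.5% is the correct power for the planned paired test in the placebo arm, so labelling it that way would be accurate. For these two endpoints the fault is an unlabelled figure rather than an arithmetic error.

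Third, the consequence is limited. These are secondary endpoints without multiplicity adjustment, the between-arm tests are worded as permissive, and the 99 patients are justified by the primary analysis in Section 13.1. All of that is true. It bears on how serious the point is, not on whether the QOL sentence is right.

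**Conclusion.** The concern holds. Taking 0.5 SD as the SD of the analysed change, at the 0.05 level and with no missing data, the stated QOL power overstates what the planned t-test delivers by about 16 percentage points two-sided (80 − 64.1) or about 5 one-sided (80 − 75.3). The inference about clinically relevant QOL changes is not supported as written. The raw-score reading reaches 80% only with a correlation the plan does not supply.

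For PFT and RP score the 80% is right for the within-arm test in the placebo arm, but it does not describe the between-arm objective in Section 3.2, for which no power is given. The point should be corrected. It does not touch the primary analysis or the sample size.

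**What to change.** Revise the three power sentences in Section 13.7 and the QOL conclusion.

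- **QOL:** state about 64% power for 0.5 SD of change, or 80% for about 0.6 SD, two-sided, at 33 versus 66. If a one-sided test is intended, say so and give about 75%, or 80% at about 0.53 SD. Reword the clinical-relevance conclusion to match.
- **PFT and RP score:** label the 80% as the two-sided within-arm paired figure for the 33 placebo patients, and add the between-arm figures (about 64% at 0.5 SD of change, 80% at about 0.6 SD).
- **All three:** name the test, the sidedness and which SD is meant. If the raw-score SD is intended, state the assumed correlation between baseline and follow-up and its basis.

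The cost is wording only: no added patients, visits or data. The price is a less favourable QOL power statement.

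### Section 13.7 commits to within-arm tests of PFT and RP score change but leaves the between-arm comparison, which is the stated objective, optional

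*Combined protocol and SAP*

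**What the plan says.** Section 3.2 sets a comparative objective: "To compare pulmonary function test (PFT) results and RP score in patients who received nintedanib versus placebo".

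Section 13.7 then gives two kinds of test for each of these endpoints.

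- **Within arm, as a commitment.** For PFT: "Changes in PFTs, relative to baseline, will be evaluated within each study arm using the Wilcoxon signed rank or paired t-tests, as appropriate". For RP score: "Changes in RP scores, relative to baseline, will be evaluated within each study arm using the Wilcoxon signed rank or paired t-tests, as appropriate".
- **Between arms, as an option.** For PFT: "Changes in PFTs may be compared between study arms using the Wilcoxon rank sum or independent sample t-tests, as appropriate". For RP score: "Changes in RP scores may be compared between study arms using the Wilcoxon rank sum or independent sample t-tests, as appropriate".

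The between-arm tests are applied to the change itself; no baseline covariate or stratification is named for them. QOL has no within-arm test, and its between-arm comparison is also worded as optional. Section 13.7 makes no multiplicity adjustment for these endpoints, and secondary analyses are run "at a significance level of 0.05". The power sentence for PFT is "With this sample sizes, we will have an 80% chance of detecting a change of at least 0.5 standard deviations", with an equivalent sentence for RP score. The arm sizes are in the OS/PFS paragraph: "With a sample size of $n = 33$ in the control and $n = 66$ in the treatment group".

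Section 13.2 says in general terms that significance tests will be stratified by chemotherapy regimen and immunotherapy exposure.

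**The concern.** A within-arm test asks whether patients in one arm changed from baseline. It does not ask whether the arms differ, which is the objective. Every patient has recently had thoracic radiation, so a change in lung function or CT score over time is plausible in both arms whatever nintedanib does.

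Within-arm significance also depends on arm size. With twice as many patients on nintedanib, the same underlying change is more likely to reach p < 0.05 there than on placebo. A report showing a significant change in one arm and a non-significant change in the other invites the conclusion that treatment made the difference. The error can go either way: a shared decline would look like harm from nintedanib, and a shared improvement like benefit. The between-arm test that would prevent this reading is the one the plan leaves optional, and its power is lower than the plan's sentence suggests.

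**Working it through.** **Inputs.** From section 13.7: 33 placebo, 66 nintedanib, level 0.05, effect 0.5 SD, stated power 80%. Assumed: two-sided testing (the section states sidedness for the log-rank test but not for PFT or RP score), complete data, and, in steps 2 and 3, a range of shared changes and of baseline/follow-up correlations that the documents do not give.

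**1. The plan's own figure.** Power from the noncentral t distribution, d = 0.5.

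- Paired test, n = 33: noncentrality 0.5 × √33 = 2.87, 32 df, power **79.5%**. This matches the stated 80%.
- Paired test, n = 66: noncentrality 0.5 × √66 = 4.06, 65 df, power 97.9%.
- Between-arm test, 33 versus 66: noncentrality 0.5 / √(1/33 + 1/66) = 0.5 / 0.2132 = 2.35, 97 df, power **64.1%** two-sided (75.3% one-sided).

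The stated 80% therefore fits a within-arm test in the placebo arm, not the comparison the objective needs. Two-sided between-arm power reaches 80% at about 0.60 SD. Detecting 0.5 SD would need about 48 + 96 patients.

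**2. Discordant within-arm results when the arms do not differ.** Let both arms have the same true change d, in SDs of change. The arms are independent, so

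P(nintedanib only) = power(66, d) × [1 − power(33, d)], and P(placebo only) = power(33, d) × [1 − power(66, d)].

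At d = 0.3: 0.670 × (1 − 0.387) = 0.411.

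| Shared change (SD) | Power, n = 33 | Power, n = 66 | Nintedanib only | Placebo only |
|---|---|---|---|---|
| 0 | 5.0% | 5.0% | 4.8% | 4.8% |
| 0.1 | 8.6% | 12.6% | 11.5% | 7.5% |
| 0.2 | 20.0% | 36.0% | 28.8% | 12.8% |
| 0.3 | 38.7% | 67.0% | 41.1% | 12.7% |
| 0.4 | 60.6% | 89.3% | 35.2% | 6.5% |
| 0.5 | 79.5% | 97.9% | 20.0% | 1.6% |
| 0.6 | 91.6% | 99.8% | 8.3% | 0.2% |

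The peak is 41.4% at 0.32 SD, and the rate is at least 20% from 0.15 to 0.50 SD. Simulation with the signed-rank test gives 28.7%, 40.9% and 21.3% at 0.2, 0.3 and 0.5 SD. With 25 versus 50 evaluable patients the rate is 38.2% at 0.3 SD and 30.8% at 0.5 SD. The between-arm t-test, simulated at shared changes of 0, 0.2, 0.3 and 0.5 SD, is falsely significant in 4.8% to 5.1% of trials.

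**3. Adjusting for baseline instead of analysing raw change.** With equal variances σ² and correlation r, change has variance 2σ²(1 − r), and the baseline-adjusted outcome has residual variance σ²(1 − r²). The ratio is (1 + r)/2.

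- r = 0.5: ratio 0.75, variance down 25%. Effective d = 0.5 / √0.75 = 0.577, power 76.5%.
- r = 0.7: ratio 0.85, variance down 15%. Effective d = 0.5 / √0.85 = 0.542, power 71.2%.

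Both compare with 64.1% for raw change.

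**The case against.** The strongest reply is that the between-arm test is in the plan. Section 13.7 names it for both endpoints, section 3.2 states the objective as comparative, and nothing says a treatment effect will be inferred by contrasting within-arm p-values. Optional wording is also the section's habit: it is used for OS, PFS and QOL, where no within-arm test competes. This stands in part. The optional wording alone does not prove that within-arm results take priority, but the plan still commits to the tests that do not answer the objective and not to those that do, and it does not label the within-arm p-values descriptive.

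Four stronger readings are tempting, and the documents do not support them.

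- *Nintedanib will often look significant on its own.* That needs a shared change of roughly 0.15 to 0.5 SD. At zero change the rate is 4.8% and symmetric, and at 0.6 SD it is 8.3%. No expected change is given.
- *The 2:1 allocation causes the discordance.* At 0.3 SD, one arm alone is significant about 54% of the time with 66 versus 33, and about 50% with 50 versus 49 (25.2% nintedanib only, 24.4% placebo only). Allocation mainly decides which arm it is.
- *Baseline is ignored.* Change scores use baseline and are valid in a randomised trial; they are only less efficient than covariate adjustment.
- *The plan intends unstratified tests.* Section 13.2 asks for stratified ones. The defect is that the tests named in 13.7 do not follow it.

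It is also fair that a linear covariate model may not suit RP score, which section 10.7 reads on a semi-quantitative 0 to 4 scale; the plan's rank-based option has merit there. The endpoints are secondary, and the primary test is untouched.

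**Conclusion.** The point holds as a mismatch between objective and committed analysis, with a risk of misinterpretation rather than a stated false inference. If both arms change equally, the chance of a nintedanib-only result runs from 4.8% at 0 SD through 41% at 0.3 SD to 8% at 0.6 SD, against 4.8%, 13% and 0.2% for placebo only. This rests on two-sided 0.05 tests, the full 33 and 66 patients, and an assumed size of shared change.

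Separately, the 80% power for 0.5 SD does not describe the between-arm comparison, which has about 64% without adjustment. Baseline adjustment would recover part of the gap, to about 76% or 71% at assumed correlations of 0.5 or 0.7. This should be changed, and it is inexpensive to change.

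**What to change.** In section 13.7:

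1. Report within-arm change in PFT and RP score descriptively, without p-values.
2. Make the between-arm comparison the definite analysis for PFT, RP score and QOL, adjusted for the baseline value and the randomisation strata, with an estimate and 95% confidence interval. This also brings 13.7 into line with the stratified testing in 13.2. For RP score, specify a rank-based or ordinal version.
3. Restate the power sentences for this test, with its sidedness: about 64% two-sided power for 0.5 SD unadjusted and 80% at about 0.6 SD, or a better figure with the assumed baseline/follow-up correlation written down.

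The cost is SAP wording and a less favourable stated detectable difference (about 0.6 SD rather than 0.5 SD if unadjusted). No new data are needed: baseline PFT, RP score and QOL and the stratification factors are already collected.

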1.4 Relevant Clinical Studies with Nintedanib

Nintedanib is being evaluated in several cancers. Additionally, nintedanib has been recently studied for the non-cancer indication idiopathic pulmonary fibrosis (IPF). A randomized Phase II placebo-controlled trial investigating the efficacy and safety of nintedanib in IPF showed that even though the primary endpoint was not met (annual rate of forced vital capacity FVC decline), there was a significant reduction in the rate of acute exacerbations seen in the nintedanib 150 mg BID treatment group compared to placebo (2.4 versus 15.7 per 100 patient-years, $p = 0.02$), improved QOL nintedanib 150 mg BID treatment compared to worsening QOL scores in the placebo group ($p = 0.007$), as well as less decline in baseline total lung capacity ($p < 0.001$) and resting oxygen saturations ($p = 0.05$) over time in the nintedanib 150 mg BID treatment compared to placebo (22). Two replicate Phase III trials (INPULSIS-1 and INPULSIS-2) were then conducted which showed that 52-week treatment with nintedanib reduced the decline in FVC compared to placebo. In INPULSIS-2, there was a significant benefit with nintedanib versus placebo in the time to first acute exacerbation ($p = 0.005$) which was not significantly different in INPULSIS-1 (23). Multikinase inhibitors similar to nintedanib such as sunitinib and sorafenib have demonstrated immunomodulatory effects through reduction of cytokines such as IL-10 and TGF- β (24,25).

As of 15 February 2013, 3556 cancer patients, over 1000 patients with IPF, and 140 healthy volunteers had been treated with nintedanib or nintedanib matching placebo, in monotherapy or in combination with chemotherapy.

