MicroRNAs (miRNAs) are crucial biological regulators of gene expression that function through suppression of their target genes and are involved in a variety of pathophysiologic processes (46,47). A TH2-like immune response with elevated mRNA levels of the transcription factor GATA-3 has been implicated in radiation-induced lung injury (48). VEGF appears to facilitate TH2-mediated lung inflammatory responses as well by reducing miR-1 expression whereas exogenous administration of miR-1 inhibited inflammatory responses and cytokine expression (49). Another experimental model shows that expression of miR-127 significantly reduced cytokine release by macrophages and attenuated lung inflammation (50). More recently, murine models of radiation-pneumonitis reveals early accumulation of CD4+FoxP3+Treg cells 21 days post-radiation (51). This also implicates GATA-3 since it transactivates TH2 cytokines, regulates FoxP3 expression and Treg function. GATA-3 activity in Tregs in turn is regulated/decreased by the transcriptional repressor Bcl6 resulting in downregulation of miR-2(52). Another thoracic radiation model reveals changes in endothelial and alveolar cell-specific gene transcripts which correlated with mi-RNA expression, such as miR-107 and miR-511 (with TLR4 expression), miR-155 (with TGF-B expression) and miR-126 (with VEGF expression).(53). We propose that the nanoparticle chip assay maybe a useful tool to measure the expression of selected miRNAs as biomarkers that may predict risk of developing radiation pneumonitis and potentially to identify patients who may benefit from nintedanib treatment in the prevention of radiation pneumonitis.

Semi-quantitative scores based on computerized tomography (CT) findings have been shown to have prognostic implications among patients with idiopathic pulmonary fibrosis or hypersensitivity pneumonitis (54,55). This study proposes to evaluate a modified RP score to compare the severity of changes in each treatment group as it correlates with QOL and pulmonary function changes.

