The complete response and complete/partial response rates will be reported by study arm and chemotherapy regimen using Wilson 95% confidence intervals. The responses rates will be compared between study arms using the CMH exact test.

The tCLN (tethered cationic lipoplex nanoparticle biochip), mCLN (microfluidic cationic lipoplex nanoparticle biochip) and qRT-PCR (real-time quantitative reverse transcription-polymerase chain reaction) measurements for the expression of miR-1, -21, -127 and -155 will be made on sera collected from NSCLC patients with and with no radiation pneumonitis. The miR expressions, vitamin D levels, and mitochondrial DNA levels will be treated as continuous and reported by radiation pneumonitis status (no versus yes) using the mean, median and standard deviation. Comparisons will be made between groups using a two-sided permutation t-test, as there is no a priori notion of which group will have higher expression.

A pilot model, using the 4 miR expression levels as the biomarker, will be built for classification of patients into 1 of 2 patient populations: radiation pneumonitis versus no radiation pneumonitis. Two classification models will be considered. The first model will treat the miR expressions as dichotomous variables, where the Youden's index method will be used to identify an appropriate threshold. The resulting threshold will maximize the correct classification rate a given miR expression alone was used to classify patients. The second model will treat the miR expressions as continuous variables. Both classification models will be constructed in a similar

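### The biomarker analyses name no treatment term, so the nintedanib-efficacy part of the exploratory objective has no analysis, and associations of post-dose mitochondrial DNA and cytokines with pneumonitis may be confounded by arm

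*Combined protocol and SAP*

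**What the plan says.** The exploratory objective in Section 3.3 has two parts: "To investigate blood-based biomarkers in evaluating risk of developing radiation pneumonitis as well as the efficacy of nintedanib". Section 1.5 adds that the miRNA assay might serve "potentially to identify patients who may benefit from nintedanib treatment in the prevention of radiation pneumonitis", which is a marker-by-treatment question.

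Section 13.7 gives the analysis. For miRNA, vitamin D and mitochondrial DNA, the values "will be treated as continuous and reported by radiation pneumonitis status (no versus yes) using the mean, median and standard deviation". The test of pneumonitis cases against non-cases is then set out: "Comparisons will be made between groups using a two-sided permutation t-test". For the logistic models, "A set of candidate variables will be obtained from miR expressions and relevant patient characteristics (demographic and clinical"), and terms are chosen "including possible two-way interaction terms, using forward selection (alpha entry = 0.05) followed by backward elimination (alpha exit = 0.05"). The modelling is then repeated with vitamin D, cytokines and mitochondrial DNA. Arm is named at none of these steps. Section 13.2 stratifies significance tests by chemotherapy regimen and immunotherapy exposure, not by arm. In the same Section 13.7, survival, quality of life, lung function, RP score and response are all reported by arm.

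The sampling schedule separates the markers. Under Sections 9.3 and 9.12.1, miRNA and vitamin D are drawn once, at Cycle 1 Day 1 or up to 7 days before dosing. Under Section 9.11, mitochondrial DNA and cytokines are drawn then too, and again at Cycles 3 and 6, when pneumonitis is suspected, and 76 to 97 days after the last dose. Section 1.5 proposes changes in these two as predictors. Section 13.7 does not say which draw enters the comparison.

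**The concern.** There are two separate issues.

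First, a stated objective has no matching analysis. Comparing markers between cases and non-cases addresses risk. It says nothing about whether the effect of nintedanib differs by marker level, or whether nintedanib changes the marker. This gap needs no assumption about drug effects.

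Second, a marker measured after dosing may be affected by treatment. The plan makes this plausible for cytokines: Section 1.4 says that similar multikinase inhibitors "have demonstrated immunomodulatory effects through reduction of cytokines such as IL-10" and TGF-β. If nintedanib also lowers the pneumonitis rate, as the design assumes, arm is related to both marker and outcome. The case group then contains relatively more placebo patients than the non-case group, and a pooled test can pick up that imbalance as if it were a biological link. A marker could be carried forward as a predictor of pneumonitis when it only records which capsule the patient took.

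**Working it through.** **Inputs.** Pneumonitis rates of 30% (placebo) and 10% (nintedanib) and a common odds ratio of about 0.26, from Section 13.1. Arm sizes of 33 and 66, from Section 13.7. Two-sided permutation t-test at 0.05, from Section 13.7. The documents give no figure for the shift that nintedanib causes in any marker, so a shift of s within-arm SD is assumed, with s from 0 to 2.

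**The plan's own figure.** (0.10/0.90) / (0.30/0.70) = 0.259, which agrees with 0.26.

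**Composition of the groups.**
- Expected cases: 33 × 0.30 = 9.9 placebo and 66 × 0.10 = 6.6 nintedanib, total 16.5.
- Nintedanib share of cases: 6.6 / 16.5 = 40%.
- Nintedanib share of non-cases: 59.4 / 82.5 = 72%.

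**Spurious difference.** Suppose the marker is unrelated to pneumonitis within each arm but shifted by s SD on nintedanib. The expected difference, cases minus non-cases, is s × (0.40 − 0.72) = −0.32 s.

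**False-positive rate.** This was simulated with normal markers, 99 complete patients, 1,500 trials per scenario and 499 permutations per trial. The last three columns are rejection rates at nominal 5%. The adjusted test centres the marker by arm and permutes within arm.

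| Assumed shift s (SD) | Difference −0.32 s | Simulated difference | Pooled test, 30% vs 10% | Adjusted test, 30% vs 10% | Pooled test, 30% in both arms |
|---|---|---|---|---|---|
| 0 | 0 | −0.01 | 5.1% | 5.9% | 4.2% |
| 0.5 | −0.16 | −0.18 | 9.5% | 6.0% | 4.9% |
| 1 | −0.32 | −0.33 | 19.7% | 4.4% | 4.9% |
| 1.5 | −0.48 | −0.46 | 30.3% | 5.3% | 3.9% |
| 2 | −0.64 | −0.66 | 41.3% | 5.3% | 4.9% |

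The Monte Carlo standard error near 5% is √(0.05 × 0.95 / 1500) = 0.6 percentage points, so the last two columns are compatible with the nominal level.

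**Which markers this reaches.** Mitochondrial DNA is in the permutation comparison and in the models. Cytokines appear only in the repeated models, where the same imbalance between cases and non-cases acts if arm is left out. miRNA and vitamin D are scheduled before treatment can act, and randomisation makes them independent of arm on average. For them s = 0.

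**Precision of a marker-by-arm term.** By a normal approximation, the variance of the interaction log odds ratio per SD is 1/(33 × 0.3 × 0.7) + 1/(66 × 0.1 × 0.9) = 1/6.93 + 1/5.94 = 0.313, so SE = 0.56. For 80% power at two-sided 0.05, the ratio of odds ratios must be near exp((1.96 + 0.84) × 0.559), about 4.8.

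**The case against.** **Most of the planned biomarker work is not confounded.** miRNA and vitamin D are baseline only, and the pilot model is built around four miRNAs. This stands. A reader might infer that every marker in Section 13.7 will look linked to pneumonitis, but the sampling schedule rules that out.

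**Even for post-dose markers, a false link is far from certain.** It needs a drug effect on pneumonitis and a drug effect on the marker. The size of the second is hypothetical: Section 1.4 speaks of related drugs and cytokines, gives no figure and says nothing of mitochondrial DNA. Even at 2 SD, more than half of trials would declare nothing. Section 13.7 might also intend the Cycle 1 Day 1 mitochondrial DNA sample, although the reference to changes in Section 1.5 points to later ones. This too stands, so the wording here is that a false link may arise.

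**Arm is not barred.** Clinical characteristics and two-way interactions could admit it to the models. But nothing requires it, and entry would depend on stepwise selection at 0.05. The permutation test has no place for arm at all, so this does not repair it.

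**A pooled association can be legitimate for prediction, and a marker may mediate the drug effect.** In that case adjusting for arm removes part of a real signal. This stands, and is a reason to show both results.

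**Stepwise selection and Youden cut-offs on about 16.5 events.** A reader might infer that reported accuracy will certainly be too good. The plan already has Firth penalisation, bootstrap, cross-validation and calibration plots for what it calls a pilot model. What it leaves unsaid is whether selection and cut-offs are repeated inside each resample. That is a secondary clarification.

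**Conclusion.** The point holds in limited form and is a modest improvement to an exploratory analysis. As written, no biomarker analysis contains treatment, so the nintedanib-efficacy part of Section 3.3 is not addressed. It would go too far to say that it cannot be answered: arm and baseline samples are recorded, so the analysis is unspecified rather than impossible. With about 16.5 expected events it would be descriptive only.

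For post-dose mitochondrial DNA and cytokines, pooling risks confounding by arm. The size is about 0.32 SD per assumed 1 SD shift. The permutation test's false-positive rate is about 10% to 41% for shifts of 0.5 to 2 SD (about 20% at 1 SD), against a nominal 5%. These figures assume the design rates, full accrual with complete data, normal markers and no within-arm association. With equal pneumonitis rates the excess disappears. miRNA and vitamin D are not affected.

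**What to change.** Amend the biomarker part of Section 13.7 as follows:

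1. State which sampling time point, or which change between time points, enters each comparison.
2. Report every marker by arm as well as by pneumonitis status.
3. For post-baseline markers, centre by arm and permute within arm.
4. Include arm as a fixed covariate in the logistic models, outside the selection procedure.
5. For each baseline marker, prespecify one marker-by-arm term and report it with its confidence interval, labelled descriptive.
6. When reporting accuracy, repeat variable selection and Youden cut-offs inside each bootstrap or cross-validation sample.

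The cost is a few SAP lines and a little more programming, with no new patients, samples or visits. There are two downsides. The interaction estimates will be imprecise. And if a post-baseline marker mediates the drug effect, the arm-adjusted result describes only the within-arm association, so the unadjusted summary can be shown beside it.
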